6. STUDY PROCEDURES

6.1 Schedule of Activities

Measure/Activity/Event	Visit 1 (Day 0)	Visit 2 (Day 1)	Day 3, 4, or 5	Day 7	Visit 3 (Day 14)	Day 21	Visit 4 (Day 28)	24-72 hours after final dose
Informed Consent Form (HIPAA/Consent/Accent)	X							
Unsecured Email Authorization Form	X							
Guidelines And Consent For Text Message Correspondence Form	X							
Mini International Neuropsychiatric Interview (MINI)	X							
Wechsler Abbreviated Scale for Intelligence-II (WASI-II)	X						X	
Edinburgh Handedness Inventory	X							
Demographics Form	X							
Childhood Trauma Questionnaire	X							
Patient Health Questionnaire (PHQ-9)		X		X	X	X	X	
Ongoing Medication Use and Changes: Initial Visit		X						
Ongoing Medication Use and Changes: Subsequent Visit				X	X	X	X	
Antidepressant Medications	X							
Any Psychotropic Medications	X							
Treatment History	X							
Alexian Brothers Urge to Self-Injure (ABUSI)		X					X	
Beck Depression Inventory (BDI-II)	X						X	
Self-Injurious Thoughts and Behaviors Interview (SITBI)	X							
Beck Scale for Suicidal Ideation (BSS)		X					X	
Inventory of Statements About Self-Injury-Lifetime (ISAS-Lifetime)	X							
Inventory of Statements About Self-Injury-Since Last Visit (ISAS-SLV)		X		X	X	X	X	
Deliberate Self-Harm Questionnaire, Part III Mood (DSHQ-M)		X					X	
Cash Choice Task		X					X	
Medication Side Effect Checklist		X		X	X	X	X	
Distress Tolerance Scale (DTS)	X							

Measure/Activity/Event	Visit 1 (Day 0)	Visit 2 (Day 1)	Day 3, 4, or 5	Day 7	Visit 3 (Day 14)	Day 21	Visit 4 (Day 28)	24-72 hours after final dose
Medication Tracking Preference Form		X						
Provided with Medication Diary (if hard copy is elected)		X			X			
MRI Safety Screen		X					X	
Urine Toxicology Screen		X					X	
Pregnancy Test		X					X	
MRI		X					X	
Blood Sample (PK and biomarkers)		X						
Provided with 32 day supply of intervention (NAC/PBO)		X						
Final dose of intervention							X	
IV catheter/ needle stick(s) and blood samples (x 3-5) (PK)							X	
Phone call (assess adverse effects, questions, concerns)		X			X		X	X
Pill count								

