Assessment of General Psychopathology and Demographic Information: We will screen for the presence of DSM-5 psychiatric diagnoses (American Psychiatric Association 2013b) at Visit 1 using the Mini International Neuropsychiatric Interview (MINI; (D. V. Sheehan et al. 1997). Clinicians formulate the diagnosis combining all clinical information. SITBI, Demographics Form, Anti-Depressant Medications form, Any Psychotropic Medications form, and Treatment History form will all be completed at Visit 1. MRI Safety Screen will be completed at Visit 2 prior to neuroimaging procedures.

All screening evaluations must be completed in 60 days from screen to Visit 2 (Day 1) and in 30 days from Visit 1 (Day 0) to Visit 2 (Day 1).

For the medication history criterion (dose stable for 1 month) the timeline will measure from date of consent (i.e. psychotropic medications dose stable 1 month prior to consent date).

An eligibility checklist will be used to fully document all pieces of eligibility. The following evaluation measures/forms will be used in screening eligibility:

- Online Screen Form
- Mini International Neuropsychiatric Interview (MINI)
- Self-Injurious Thoughts and Behaviors Interview (SITBI)
- Antidepressant Medications
- Any Psychotropic Medications
- Treatment History Form
- MRI Safety Screen
- Inventory of Statements About Self-Injury-Lifetime (ISAS-Lifetime)
- Eligibility Checklist

The following table outlines each visit and measure used to assess each eligibility criterion:

Table 2 – Screening Measures and Visits

Criterion Assessed	Inclusion/Exclusion	Visit/Event	Measure/Form/Survey
16-24 years old	Inclusion	Online screening	Online Screen
Female	Inclusion	Online screening	Online Screen
Generally medically healthy	Inclusion	Online screening	Online Screen
At least 1 NSSI episode in past 2 months	Inclusion	Online screening	Online Screen
		Visit 1	SITBI
			ISAS-Lifetime
≥ 5 past episodes of NSSI with significant tissue damage (e.g. skin is broken or bruised, and/or scars resulted from the injury)	Inclusion	Online screening	Online Screen
		Visit 1	SITBI
			ISAS-Lifetime
Psychotropic medications are dose-stable for 1 month.	Inclusion	Online screening	Online Screen
		Visit 1	Antidepressant Medications
			Any Psychotropic Medications
Any MRI contraindications (e.g. metal plates, claustrophobia, braces, implanted devices)	Exclusion	Online screening	Online Screen
		Visit 2	MRI Safety Screen
		Visit 4	
Male	Exclusion	Online screening	Online Screen

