6.2.2 Enrollment, Baseline, and/or Randomization

Enrollment

Enrollment will be defined as the time at which the participant is randomized. Consent will occur at Visit 1 (Day 0). Randomization will occur after Visit 1 (Day 0), when it is confirmed that all eligibility criteria are met, and before Visit 2 (Day 1). There will be a maximum 30-day window between Visit 0 and Visit 1. Enrollment date will be recorded in OnCore (subject specific calendar), and Enrollment Log.

Baseline Assessments

Visit 1 (Day 0) Initial Assessments:

- Mini International Neuropsychiatric Interview (MINI)
- Self-Injurious Thoughts and Behaviors Interview (SITBI)
- Edinburgh Handedness Inventory
- Demographics Form
- Anti-Depressant Medication Form
- Any Psychotropic Medication Form
- Childhood Trauma Questionnaire (CTQ)
- Beck Depression Inventory-II (BDI-II)
- Inventory of Statements About Self-Injury (ISAS-Lifetime)
- Distress Tolerance Scale (DTS)

Visit 2 (Day 1) Baseline Assessments/Activities:

- Beck Scale for Suicidal Ideation (BSS)
- Patient Health Questionnaire-9 (PHQ-9)
- Alexian Brothers Urge to Self-Injure (ABUSI)
- Deliberate Self-Harm Questionnaire, Part III Mood (DSHQ-M)
- Cash Choice Task
- Side Effect Checklist
- Ongoing Medication Uses and Changes: Initial Visit
- MRI safety screen
- Blood draw
- Urine toxicology screen
- Pregnancy test
- Neuroimaging procedure (MRI brain scan)

- Wechsler Abbreviated Scale for Intelligence-II (WASI-II)

Intervention dispensed with instructions (32-day supply)

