9.4 Interim Analyses and Stopping Rules

The following safety findings would prompt temporary suspension of enrollment and

study intervention until a complete safety review is convened:

- Suicide attempt in greater than 20% of participants that have received study intervention beginning when at least 10 participants have received study intervention.
- Suicide attempt in greater than 30% of participants that have received study intervention when between 1 and 9 participants have received study intervention.
- SAE in greater than 30% of participants to receive study intervention
- SAE occurrence in first 3 participants to receive study intervention
- AE indicating anaphylaxis to study intervention in at least 30% of participants to receive study intervention beginning when 10 participants have received intervention
- Suicide completion in at least 2 participants to receive study intervention
- Anything else deemed a safety risk to participants by the investigator or the IMC

“Study intervention” refers to any or all 3 of the treatment groups. The following safety findings would prompt an ad hoc safety review without suspension of enrollment and study intervention:

- NSSI frequency in past month increase of 100% in any single participant as determined by SITBI (question 148), comparing Day 1 and Day 28 – 32 assessments.
- Average NSSI frequency in past month increase of 50% during study enrollment as determined by SITBI (question 148, NSSI section, “How many times in the past month?”) comparing Day 1 to Day 28 - 32 measurement beginning when 5 participants have received study intervention.
- Suicide completion in 1 participant to receive study intervention

A safety review will be carried out by the Independent Monitoring Committee and its occurrence would be reported to Advarra IRB and NCCIH. Safety findings such as those listed above will be presented to Independent Monitoring Committee to review the events by blinded group to determine whether there are statistical as well as clinical concerns. The objective of the safety review is to determine whether the study or intervention (NAC) for an individual or for the study cohort should continue per protocol, proceed with enhanced monitoring, be further investigated, be discontinued, or be modified and then proceed. Suspension of enrollment is a potential outcome of a safety review.

Outside of safety reviews, no interim analyses are planned for this study.

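### Both NSSI-worsening review rules in section 9.4 compare SITBI question 148 at Day 1 and Day 28–32, but the visit schedule has the SITBI at Day 0 only, so neither rule can be evaluated as written

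*Combined protocol and SAP*

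**What the plan says.** Section 9.4 introduces three rules with "The following safety findings would prompt an ad hoc safety review without suspension of enrollment and study intervention". Two concern self-injury frequency and one concerns a single completed suicide. The individual rule is "NSSI frequency in past month increase of 100% in any single participant as determined by SITBI (question 148), comparing Day 1 and Day 28" (to 32). The cohort rule is a 50% rise in average past-month frequency on the same SITBI question, "comparing Day 1 to Day 28 - 32 measurement beginning when 5 participants have received study intervention". Each rule thus fixes an instrument, an item, a past-month recall period and two visits.

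The sections on data collection say otherwise. In 6.1, the row "Self-Injurious Thoughts and Behaviors Interview (SITBI") is marked once, at Visit 1 (Day 0). Section 6.2.1 agrees: "SITBI, Demographics Form, Anti-Depressant Medications form, Any Psychotropic Medications form, and Treatment History form will all be completed at Visit 1". In 6.2.2 the SITBI is in the Visit 1 list and absent from the list headed "Visit 2 (Day 1) Baseline Assessments/Activities". The itemised Visit 4 list in 6.2.5 omits it too. The 6.2.5 narrative still mentions an abbreviated SITBI at the final visit, reworded to cover the interval from the previous clinical assessment.

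The self-injury measure that is repeated is the "Inventory of Statements About Self-Injury-Since Last Visit (ISAS-SLV"), marked in 6.1 at Days 1, 7, 14, 21 and 28. Neither rule uses it.

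**The concern.** A numeric safety trigger works only if both measurements it compares are taken. Here the Day 1 value is never collected, and the final-visit value is either not collected or collected over a different recall period. Followed to the letter, the protocol gives nobody the data to say whether either threshold was crossed.

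Every participant enters with recent self-injury (4.1), and the sponsor chose to have the Independent Monitoring Committee (IMC) look when it rises by set amounts. Section 7.6 schedules the first IMC meeting 6 months after enrolment starts and the next a year later, so ad hoc triggers matter in between. What is at stake is that planned review. No efficacy result depends on it.

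**Working it through.** **Step 1. What the rules need against what is scheduled.**

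| Source | Day 0 | Day 1 | Final visit |
|---|---|---|---|
| 9.4, both rules need | not used | question 148, past month | question 148, past month |
| 6.1 schedule | SITBI | none | none |
| 6.2.1 text and Table 2 | SITBI | none | none |
| 6.2.2 visit lists | SITBI | none | not covered |
| 6.2.5 itemised list | not covered | not covered | none |
| 6.2.5 narrative | not covered | not covered | abbreviated form, different recall |

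Participants scheduled to have past-month question 148 at both named visits: 0 of up to 46 enrolled, or 0 of 36 planned completers (4.3). Rules affected: 2 of the 3 in the ad hoc list. Taking the 6.2.5 narrative at face value does not change this, because the Day 1 value is still missing and the recall period does not match.

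The conflict is between current sections. The revision summaries for versions 9 and 11 (SITBI moved to Day 0, then dropped from Visit 4) only explain how 9.4 was probably left behind.

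**Step 2. Would the Day 0 SITBI serve as baseline?** Only partly. Day 0 may precede Day 1 by up to 30 days (6.2.2). Take a past month as M = 28 to 31 days (assumption) and the gap as g days. The Day 0 window then overlaps the month before first dose by max(0, M − g) days:
- g = 30: 0 to 1 day
- g = 14 (assumed): 14 to 17 days

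**Step 3. Would a past-month item at the final visit cover treatment?** Dosing starts on Day 1. A final visit on Day D is D − 1 days later, and the item misses max(0, D − 1 − M) treatment days:
- Day 28 (27 days later): 0 missed
- Day 32 (31 days later): 31 − 31 = 0 to 31 − 28 = 3 missed
- Day 35, the rescheduling limit in 6.2.5 (34 days later): 34 − 31 = 3 to 34 − 28 = 6 missed

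The item therefore suits the purpose if it is asked.

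**Step 4. Would raw ISAS-SLV totals do instead?** Not without standardising. Reading the Day 1 form by its name, it covers only the Day 0 to Day 1 gap g. The later forms together cover 27 to 34 days. At a constant self-injury rate the apparent change is (treatment days ÷ g) − 1:
- g = 7: 27/7 − 1 = +286% to 34/7 − 1 = +386%
- g = 14: 27/14 − 1 = +93% to 34/14 − 1 = +143%
- g = 30: 27/30 − 1 = −10% to 34/30 − 1 = +13%

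The gaps are assumed values. With a short gap, the +50% and +100% thresholds could be met with no true change. This bears on the choice of repair and is not an error in the plan.

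**Step 5. Zero baseline.** Section 4.1 asks for one episode in the past two months, so a past-month count of 0 is possible, and a percentage increase from 0 is undefined.

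**The case against.** The strongest reply is that this is loose wording with little consequence. Day labels are not used strictly: the 6.2.2 narrative puts the baseline Side Effect Checklist at Day 0, while 6.1 puts it at Day 1. So Day 1 in 9.4 may simply mean baseline, and a Day 0 SITBI exists. That reading supplies one side of the comparison, but there is still no past-month value at the final visit.

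Other safeguards do remain:
- The study team reviews the ISAS-SLV and PHQ-9 weekly (7.2), and the Independent Clinical Monitor reviews all adverse events.
- Section 8 covers self-injury needing urgent care. Supplement IV responds to markedly more frequent or more severe self-harm.
- Self-injury leading to admission is an SAE and counts toward "SAE in greater than 30% of participants to receive study intervention".
- The IMC can request interim reports (6.2.3), receives unanticipated problems within 7 or 14 days, reviews related events unresolved two weeks after stopping drug, and gets an annual summary. Section 9.4 also has a catch-all clause.

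This limits the harm, but none of these routes applies a numeric self-injury threshold, and several rest on judgement.

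It is also true that both rules need a final-visit value, so even when repaired they cannot protect that participant during dosing. They would still inform the IMC about the cohort and about participants enrolled later.

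Finally, Table 1 in section 3 still allows Day 28 plus or minus 3 days. A Day 25 visit is 24 days after Day 1, which lowers the bottom of the Step 4 ranges to 24/7 − 1 = +243%, 24/14 − 1 = +71% and 24/30 − 1 = −20%. That is correct and leaves the main point unchanged.

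**Conclusion.** The concern holds. Two of the three ad hoc review rules in 9.4, and the only ones based on NSSI frequency, cannot be evaluated as written. This rests on comparing sections of the current protocol and on no numerical assumption. The assumed month length and visit gaps affect only how the repair should be worded. The consequence is moderate: a planned IMC review would not be triggered by its own criteria. These rules never suspend enrolment or treatment, related data are collected, and the primary analysis is unaffected. It should be fixed, since a stated safety rule cannot operate and the repair is cheap.

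**What to change.** **Option A (preferred; keeps the thresholds and recall period).** Ask question 148 alone at Day 1 and at the final visit (Day 28–32, up to Day 35). One item rather than the interview respects the decision to drop the SITBI from Visit 4 for burden, and Day 1 is a better baseline than Day 0. Cost: one question at two existing visits.

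**Option B (no added assessment).** Rewrite both rules on the ISAS-SLV. Fix the Day 1 recall at 28 days and express both periods as episodes per 28 days. Add the ISAS-SLV to the Visit 2 list in 6.2.2, which omits it although 6.1 and the 6.2.2 narrative include it. Cost: a fixed recall period at Day 1 and reworded rules.

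Under either option:
- State what happens when the baseline count is 0, for example an absolute count that triggers review.
- State that the cohort rule compares mean counts and does not average individual percentage changes.
- Align 6.1, 6.2.2, 6.2.5 and 9.4, including the abbreviated SITBI sentence in 6.2.5.

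A minor correction can go in the same amendment. Section 7.1 says the BSSI and BDI-II are given at baseline and Weeks 1 to 4, but 6.1 has the BSS at Days 1 and 28 and the BDI-II at Days 0 and 28. Optionally, extend the automatic email in 7.2 to the PHQ-9 suicidal-thinking response at Days 7, 14 and 21, which would add some alerts to handle.

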9.5 Outcomes

9.5.1 Primary Outcome

- 1) GSH concentration in ACC voxel. Resolution of reduced versus oxidized GSH using spectroscopy is not possible; GSH concentrations as measured by MRS represent primarily reduced, intracellular GSH. Collected during neuroimaging procedures at Visit 2 and Visit 4.

9.6 Data Analyses

To address the study objectives, we will quantify the within-person percent change in proposed primary biological signature: brain GSH. We will fit a general linear model with brain GSH as dependent variable with group (NAC high vs NAC low vs PBO) as the predictor variable of interest. Since we apply a minimization procedure to ensure that groups are similar on key demographic and baseline clinical variables (age, baseline NSSI severity, presence of concurrent psychotropic medication), as is typically done in a large clinical trial we will not include covariates. Should the primary outcome values be highly skewed, we will use non-parametric tests instead to compare groups. We will use the standardized Wilcoxon test statistic with the Dwass, Steel, Critchlow-Fligner (DSCF) multiple comparison analysis. This analysis takes each pair of groups, one pair at a time (high NAC vs. low NAC; high NAC vs. placebo; low NAC vs. placebo), computes a Wilcoxon test statistic to compare the two groups in that pair, and obtains a pvalue that is analogous to Tukey's control of family-wise Type I error (the test statistic is scaled to Tukey's studentized range distribution) (Hollander and Wolfe, 1999). This analysis to compare the 3 treatment groups on the primary outcome will adjust type I error using Tukey's procedure for the 3 pairwise comparisons among the 3 groups. Tukey's procedure is less conservative than the Bonferroni adjustment used in the sample size/power

calculation, hence we expect slightly higher power than planned. We will quantify the effect size of each group's change to determine next steps with the research.

To assess the robustness of our conclusions about the primary outcome to participants whose medical profile changes during the course of active treatment in our study, we will conduct sensitivity analyses. For example, if participant(s) need to have a change in their non-study medications during our study, they will remain in the study but the changes in medications will be noted in the study database. We will repeat our primary analysis excluding such people to see if our conclusions remain the same. We note, however, that this analysis is not protected from bias by the randomization.

To address the secondary study objectives of exploring additional potential biosignatures, we will fit similar general linear models with each of the additional outcomes (brain Glu, blood GSH/GSSG, antioxidant protein levels, GABA concentrations, amygdala-insula functional connectivity) as dependent variables, with group (NAC high vs NAC low vs PBO) as the predictor variable of interest, again without including covariates to preserve power. These secondary analyses will use Holm's step-down Bonferroni type I error correction to adjust for both multiple comparisons among groups and multiple testing across the several secondary outcomes.

Data analysis: To address the secondary outcome of NAC PK, NAC and GSH concentration-time data will initially be analyzed by non-compartmental methods. WinNonLin Phoenix (Pharsight®) will be used to calculate the partial NAC area under the curve (AUC_0-2h) using the linear trapezoidal rule and maximum concentration (Cmax). The AUC_0-2h and Cmax for GSH will also be calculated. Descriptive statistics of the PK parameters will be determined. Drug concentrations and other PK variables will be correlated with degree of change in biological signatures.

To address the secondary objective of describing the tolerability of oral NAC at the proposed study doses, we will quantify rates of side effects and other adverse events and compare rates between groups using Poisson, survival, or other rate-based models as appropriate for each event type.

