1. STUDY OBJECTIVES

1.1 Primary Objective

To test the hypothesis that oral NAC treatment (but not placebo) will lead to at least a 5% increase in glutathione (GSH) concentrations in the anterior cingulate cortex as measured by magnetic resonance spectroscopy (MRS) in a study of 36 adolescents and young adults with NSSI.

We will test two NAC doses (3600mg and 5400mg). Dose superiority will be defined both by change in GSH and by tolerability. Specifically, the superior dose will be the one which showed capability of achieving the greatest increase in GSH in the ACC as measured by MRS, and where no more than 20% of subjects at that dose discontinue or diminish their dose due to medication adverse effects (See section 5.1 for adverse effects and diminishing dose). (In other words, no less than 80% of subjects at a dose can discontinue or diminish their dose due to adverse effects in order to qualify as a superior dose.)

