9. STATISTICAL CONSIDERATIONS

9.1 General Design Issues

The goals of this study are to test whether significant change can be found in candidate biological signatures after 4 weeks of oral NAC. Three groups are used to compare pre-post treatment changes in those who received NAC 5400mg/day, 3600mg/day, or PBO.

Primary Hypothesis:

- 1) NAC high dose and/or NAC low dose (but not PBO) will increase cortical GSH by at least 5%

Secondary Hypotheses:

- 1) NAC high dose and/or NAC low dose (but not PBO) will decrease cortical GLU by at least 5%
- 2) NAC high dose and/or NAC low dose (but not PBO) will increase blood GSH/GSSG by at least 50%
- 3) NAC concentrations (using data from both dose groups) will be correlated with clinical and neuroimaging outcomes.
- 4) NAC high dose and/or NAC low dose (but not PBO) will increase resting-state functional connectivity between amygdala and insula
- 5) NAC high dose and/or NAC low dose (but not PBO) will increase ACC GABA.
- 6) NAC high dose and/or NAC low dose (but not PBO) will increase antioxidant protein levels (catalase and heme oxygenase-1 [HO-1]).
- 7) Higher-dose NAC will show larger changes in all of the biological signatures listed above compared to lower-dose NAC
- 8) While both NAC doses will be acceptable to most patients, lower-dose NAC will be better tolerated than higher-dose NAC.

Primary outcome measures:

- 1) GSH concentration in ACC

Secondary outcome measures:

- 1) Blood GSH/GSSG (the reduced-to-oxidized GSH ratio in blood)
- 2) Glu concentrations in ACC
- 3) Tolerability of NAC as measured using a side effects checklist
- 4) Pharmacokinetic analysis of NAC and its metabolites, CYS and GSH
- 5) Antioxidant protein levels (catalase and heme oxygenase-1 [HO-1]) for which

previous studies have shown increases following NAC treatment.

- 6) GABA concentrations in the ACC. Our pilot study found a significant increase in GABA levels after 28 days of oral NAC (6000 mg/day) ([name] et al. 2018).
- 7) Functional connectivity between amygdala and insula. Our pilot study showed that after treatment with oral NAC (3600 mg/day), participants with NSSI showed an increase in amygdala functional connectivity in a cluster that included the bilateral insula.

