9.2 Sample Size and Randomization

The sample size (n=12 per group) was selected based on calculations on biosignature data from the oral NAC pilot study in adults with either Parkinson's disease (PD; n=5) or healthy controls (HC; n=3). Using variability estimates from this study, we found that with groups of 11 (assuming one drop-out per group), we would have 80% power to show a significant ($\alpha=0.0167$, Bonferroni corrected for 3 pairwise comparisons) effect of NAC high vs. NAC low vs. PBO on our primary outcome of brain GSH if the variability is similar to healthy controls seen in our pilot work (detectable mean group difference in pre-dose to post-dose percent change of 2.95%, expected mean group difference ~4.83%). The data collected in the R61 will serve to provide the variability information needed to design a future, confirmatory clinical trial.

Treatment Assignment Procedures

Randomization and Double-Blind: Participants who meet criteria for entry into the study (based on the online screen and the clinical interview) and who provide consent will be randomized to active NAC low dose versus NAC high dose versus PBO (1:1:1). We will implement an adaptive randomization procedure called minimization. The purpose of the procedure is to ensure that the 3 groups are similar with respect to key demographic and clinical variables such as age, NSSI severity and medication use. See Section 6.2.2 for a complete description of the randomization procedure.

All participants, family members, and study staff (including the study statistician) will be blinded to treatment assignment. The research pharmacy, IDS, will be the only unblinded entity. See Section 6.2.2 for a complete description of the blinding (and unblinding) procedures.

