9.3 Definition of Populations

The Intent to Treat population will include all those who completed both baseline and 4-week MRI scans and blood draws, even those who discontinued the study medication due to intolerance or other reasons. The Per-Protocol analysis population will consist of only those subjects who completed all procedures.

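### Section 9.6 models brain GSH and the secondary biomarkers on treatment group alone, and its reasons do not justify leaving out each outcome's own baseline

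*Combined protocol and SAP*

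**What the plan says.** Section 9.6 opens with the quantity of interest: "we will quantify the within-person percent change in proposed primary biological signature: brain GSH". The next sentence gives the model: "We will fit a general linear model with brain GSH as dependent variable", with treatment group as the predictor of interest. It names neither a timepoint nor a change. Covariates are excluded because minimisation makes the groups similar on age, NSSI severity and medication, and because "as is typically done in a large clinical trial we will not include covariates". The other biomarkers get similar models, "again without including covariates to preserve power".

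Other sections bear on this:

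- **Randomization (6.2.2):** the minimisation factors are age group, NSSI severity category and antidepressant use. Assignment takes place after Visit 1 and before Visit 2, the visit at which the first scan and blood sample are taken.
- **Sample size (9.2):** power is stated for 11 per group at alpha 0.0167, with a "detectable mean group difference in pre-dose to post-dose percent change of 2.95%, expected mean group difference ~4.83" percent. The variability is that of the healthy controls in a pilot study, of whom there were three.
- **Objective (1.1):** NAC "will lead to at least a 5% increase in glutathione (GSH) concentrations in the anterior cingulate cortex". Section 9.1 repeats the 5% threshold.
- **Populations (9.3):** the analysis set is "all those who completed both baseline and 4-week MRI scans and blood draws".
- **Connectivity:** 9.6 plans a group-only linear model. Supplement II plans repeated-measures ANOVAs on z-scores.

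**The concern.** For a continuous outcome measured before and after treatment, the baseline value of that outcome is usually the most useful covariate. Here it enters at most as the divisor of a percent change. The three reasons in 9.6 concern something else:

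- **Minimisation** balances clinical factors. It does not balance baseline GSH, and could not, because GSH is first measured after assignment.
- **Large-trial practice** is not a guide for about 36 people. With 12 per group the difference in baseline means between two groups has a standard error of √(2/12) = 0.41 SD. The chance that a given pair differs by more than 0.5 SD is therefore about 22%.
- **Preserving power** is a fair reason to omit several weak factors in a trial this small. It is not a reason to omit one covariate that costs one degree of freedom and may explain part of the variance.

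What is at stake is the precision of the group differences and of each group's estimated change, which the plan will use to decide next steps. There is also a gap in wording: the model sentence does not say that the dependent variable is percent change, and the secondary models inherit that gap.

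**Working it through.** **Inputs from the documents (9.2).** 11 per group; 80% power; alpha 0.0167 = 0.05/3; detectable difference 2.95 points; expected difference about 4.83 points. No SD, pre-post correlation (ρ) or between-person SD is given. Two-sided testing is assumed, and ρ is shown over a range.

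**Step 1: the implied SD.** The 2.95 cannot be checked independently without an SD, so I solve for the SD that yields it. For a two-group t test with df 20, two-sided alpha 0.0167 and 80% power, SD = 1.98 points. The noncentrality is 2.95 / (1.983 × √(2/11)) = 3.49.

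**Step 2: the planned analysis.** Section 9.6 uses Tukey's adjustment. With three groups and 30 residual df the critical value on the t scale is 2.465. Power for one pair, using percent change on group alone, is 84.0% at 2.95. At 4.83 the noncentrality is 4.83 / (1.983 × √(2/11)) = 5.71 and power is about 99.9%.

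**Step 3: adding baseline.** Assume equal variance s² at the two visits.

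- Variance of change: 2s²(1 − ρ).
- Residual variance after adjusting for baseline: s²(1 − ρ²).
- Ratio of the second to the first: (1 + ρ)/2.

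Residual df fall from 30 to 29 and the critical value rises to 2.470. The variance of a group difference is SD² × (1 + ρ)/2 × [2/11 + (difference in baseline means)²/Sxx], where Sxx is the pooled within-group sum of squares of baseline. Power is averaged over random baseline draws. The between-person SD implied by each ρ is 1.98/√(2(1 − ρ)).

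| ρ (assumed) | 0.3 | 0.5 | 0.7 | 0.9 | 0.98 |
|---|---|---|---|---|---|
| Between-person SD, % of mean, at SD 1.98 | 1.7 | 2.0 | 2.6 | 4.4 | 9.9 |
| Power at 2.95, SD 1.98: group only | 84.0 | 84.0 | 84.0 | 84.0 | 84.0 |
| Power at 2.95, SD 1.98: with baseline | 95.6 | 92.4 | 88.6 | 84.5 | 82.9 |
| Power at 4.83, SD doubled to 3.97: group only | 65.3 | 65.3 | 65.3 | 65.3 | 65.3 |
| Power at 4.83, SD doubled to 3.97: with baseline | 83.7 | 77.5 | 71.5 | 66.0 | 63.9 |

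The gain disappears above ρ of about 0.92. At ρ 0.99 power falls from 84.0% to 82.7% at SD 1.98, and from 65.3% to 63.7% at doubled SD. Direct simulation of lognormal data with a log-scale model gave the same pattern, and per-pair error under the null was 1.9 to 2.1% with or without baseline.

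**Step 4: how firm the SD is.** With three healthy controls there are 2 df. A chi-square 95% interval around 1.98 runs from about 1.0 to 12.5 points, so a doubled SD is well within reach.

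**Step 5: the unnamed dependent variable.** If Day 28 GSH alone were modelled on group, its SD would be 1.98/√(2(1 − ρ)). Power at 4.83 would then be 100.0, 99.9, 97.0, 54.2 and 10.7% at the five correlations, against about 99.9% for percent change.

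**The case against.** The strongest reply is that nothing here is invalid. Percent change already uses each person's baseline, and randomisation protects a group-only comparison of it. At the plan's own expected effect and implied SD, power is about 99.9% with or without adjustment. The documents give no correlation, so they cannot show how large the gain would be, or even that there would be one. A gain of 8 points or more at 2.95 needs a between-person SD of about 2% of the mean or less; above about 5% the gain turns into a small loss. All of this stands, and it keeps the point to one of precision.

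A reader might infer from the model sentence that Day 28 GSH alone is the planned outcome, and that the trial could have the very low power of step 5. The documents do not support that. The sentence before it, the 5% hypothesis and the power calculation all work in percent change, and Day 28 values alone cannot test a 5% increase. A few words cure this gap, and it is not an argument for baseline adjustment. The two effects barely overlap in any case: the Day 28 reading fails at high correlations, where adjustment gains almost nothing over percent change.

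It is also fair that a log-scale model should not be left without a plan for skewed data. The fix therefore keeps the plan's rank-based procedure.

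What the reply does not rescue is the reasoning in 9.6. Neither minimisation nor large-trial practice covers the outcome's own baseline, and the cost in power is at most about 1 to 2 points.

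**Conclusion.** The point holds as a matter of possible lost precision and incomplete specification. It should be fixed, but it does not threaten validity. A reader might infer bias or an inflated type I error from the missing covariate; neither follows, because assignment is randomised and the group-only test keeps its error rate.

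The size depends on quantities the plan does not report. At 2.95 points and SD 1.98, adjustment is worth about 12 points of power at a correlation of 0.3 (95.6 against 84.0), under 1 point at 0.9, and costs about 1 point at 0.98. At 4.83 points and SD 1.98 it makes no practical difference. At 4.83 points and a doubled SD it is worth about 18 points at 0.3 (83.7 against 65.3) and about 6 at 0.7 (71.5 against 65.3). These figures assume equal variances at the two visits, 11 per group, Tukey's adjustment and one pairwise comparison. Confidence is moderate, because the SD is back-solved and the correlation is assumed.

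Two differences of wording are minor and are not part of this point: the medication factor is described differently in 6.2.2 and 9.6, and 6.2.2 says handedness will enter the analysis without naming a model.

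**What to change.** Before unblinding, amend 9.6 and Supplement II as follows.

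1. **Dependent variable.** State that the primary model analyses within-person change in ACC GSH from baseline to the final visit, on the percent or log-ratio scale, and not the Day 28 concentration alone.
2. **Covariate.** Add the outcome's own baseline as the single covariate in the primary and secondary biomarker models. For GSH, for example, fit log(Day 28/baseline) on group plus centred log baseline. Report the Tukey-adjusted group differences back-transformed to percent, and each group's adjusted change with its confidence interval, so that the 5% hypothesis can be judged. The secondary outcomes keep their Holm correction.
3. **Sensitivity and fallback.** Keep group-only percent change as a sensitivity analysis. Keep the Dwass, Steel, Critchlow-Fligner procedure, applied to percent change, as the fallback if values are highly skewed.
4. **Connectivity.** Analyse it on the raw z-score scale with its own baseline, since percent change is unsuitable for a score that can be near zero or negative. Reconcile the group-only linear model in 9.6 with the repeated-measures ANOVA in Supplement II so that one model is named.

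The cost is SAP wording. The baselines are already collected and 9.3 already requires both scans and both blood draws, so no analysed participant is lost for want of a baseline. The model uses one residual df (33 to 32 with 36 analysed, 30 to 29 with 33). The downside is at most about 1 to 2 points of power if the pre-post correlation is very high.
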